2.2 Sample Size Justification

Part 1: A sufficient number of subjects will be screened and entered into Part 1 to provide the number of subjects required in Part 2.

Part 2: A total of up to 22 subjects will be randomized to complete approximately 20.

In a non-inferiority test on MV at 5min from a 4 period, 2 treatment replicate cross-over design, a total sample size of 20 would achieve >90% power at a 2.5% significance level (1-sided) when the true difference between the means is 0.8L/min, the non-inferiority margin is -0.5L/min, and the within-subject standard deviation is 1.2L/min.

In a superiority test on MV at 5min from a 4 period, 2 treatment replicate cross-over design, a total sample size of 20 would achieve 83% power at a 2.5% significance level (1-sided) when the true difference between the means is 0.8L/min and the within-subject standard deviation is 1.2L/min.

The planned sample size is adequate for sequential testing of noninferiority followed by superiority.

3 Study Objectives

3.1 Primary Objectives

- To assess the change in minute ventilation at 5 minutes of intramuscular nalmefene and intranasal naloxone reversal from the opioid induced nadir

3.2 Secondary

- To assess the time course of changes in minute ventilation of intramuscular nalmefene and intranasal naloxone reversal from the opioid induced nadir
- To evaluate the pharmacokinetics of nalmefene and naloxone following various routes of administration
- To assess the safety and tolerability of fentanyl when co-administered with and without nalmefene or naloxone

3.3 Exploratory

- To characterize the time course (Magnitude of change in minute ventilation) of intramuscular nalmefene and intranasal naloxone reversal from the opioid induced nadir

4 Study Endpoints and Evaluations

4.1 Pharmacokinetic Endpoints and Evaluations

Pharmacokinetic concentration and endpoint will be included in a separate data analysis plan (DAP) and will not be included in this SAP.

4.2 Pharmacodynamics Evaluations

Pharmacodynamic (PD) evaluations will be performed for the following time frames: prior to fentanyl, after fentanyl and before any antagonists, and after antagonist administration (nalmefene, naloxone). The PD variables include:

- Minute Ventilation (MV) in L/min - calculated as the product of tidal volume and respiratory rate, determined in a continuous fashion by noninvasive respiratory volume monitor
- Transcutaneous CO₂ (TCO₂) in mmHg – a lagging measure of respiratory status in OIRD, it is an exploratory supplement endpoint to MV

4.3 Safety Endpoints and Evaluations

Safety will be assessed using

- Treatment emergent adverse events (TEAEs)
- Clinical laboratory test results
- Vital signs, including SpO₂
- Physical examinations
- Conventional 12-lead ECGs
- Local tolerability

4.4 Other Evaluations

Other evaluations include:

- Demographics and baseline characteristics
- Disposition
- Study drug dosing

- Medical history
- Drug screen
- Pregnancy test
- Medications (prior and concomitant)

5 Analysis Populations and Applications

For purposes of analysis, the following analysis populations are defined:

5.1 Enrolled Population

Enrolled population includes all subjects who signed informed consent.

5.2 Randomized Safety Population

Randomized safety population, also known as the safety population, includes subjects who are randomized and receive at least 1 dose of the study drug.

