Vital signs and SpO ₂ with HDYF?	X	X	X	X	X	X	X		Taken after 5 minutes seated (or during infusions when supine, seated, or semirecumbent): heart rate, blood pressure, respiratory rate, SpO ₂ Screening: Additional standing (for ~2 minutes) vital signs (heart rate and blood pressure) Days 1, 4, 7, 10: During fentanyl infusion: Predose (-15 minutes), end of infusion, 2 and 4 hrs post end of infusion. Time points may be added, omitted, or adjusted. Vital signs also taken pre- and post-naloxone challenge test.
Oral temperature	X	X	X	X	X	X	X		For safety purposes, forehead temperature may be substituted for oral. Days 1, 4, 7, 10: Predose, and 8-12 hrs post infusion. Time points may be added, omitted, or adjusted.
Respiratory monitoring/PD training and practice session	X	X							May be performed at screening or Check-in Day -1 or both.
Randomization			X						Prior to study drug dosing in Period 1 only

Phase	Screen-ing	Treatment						F/U	Notes
Period	Screen-ing	Check-In	1	2	3	4	EOS	F/U	
Study Day	-29 --2	-1	1	4	7	10	11	18-21	
Study Procedures									
Fentanyl Infusion administration			X	X	X	X			Time is relative to start of IV infusion. 3-step fentanyl infusion: first infusion at an initial rate of 5.0 mcg/min, a second infusion for 20 min and a third infusion up to 90 min, see Table 7 .
Nalmefene or Naloxone Study drug dosing			X	X	X	X			Nalmefene or Naloxone will be administered approximately 10 min following the start of Fentanyl Infusion #2. Time = 0, relative to other procedures.
Local Tolerability			X	X	X	X	X		Nalmefene Treatment only, Days 1, 4, 7, 10: Prior to the start of IV infusion Relative to Nalmefene administration: 15, 30 minutes, 1 hr and 24 hr after nalmefene administration.
Blood sample for drug concentration			X	X	X	X			Relative to Nalmefene/Naloxone administration: 2.5, 5, 10, 15, 20, and 30 minutes and at 1, 2, 4, 8, 12, and 24 hours after nalmefene/naloxone administration.
Respiratory volume monitoring and capnography			X	X	X	X			Relative to fentanyl infusion, Predose (baseline) and continuous RVM throughout dosing and for 1 hr after the end of the infusion for fentanyl. Time interval may be adjusted, or specific time points or multiple shorter intervals may be selected.

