5.3 Eligible Analysis Set (EAS)

Twenty subjects will be expected to complete the study, each of whom will receive nalmefene or naloxone in different order after fentanyl -induced respiratory depression (OIRD).

For each period, eligible analysis set (EAS) include subjects/periods who are randomized, receive study drug, have at least 1 valid PD measurement, and their OIRDs are worse than baseline for MV and TCO₂. Note: baseline and OIRD for MV and TCO₂ may be different. Therefore, eligible analysis set for each PD parameter and period may be different.

To evaluate the treatment difference between nalmefene and naloxone, the same treatment under different periods will be pooled by averaging PD parameters from eligible data for each subject.

This analysis set will be used as primary analysis.

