8.1 Adverse Events

Adverse events (AEs) will be presented separately by treatment assignment. AEs will be coded using the most current version of MedDRA and will be classified by SOC and PT of MedDRA. Severity of AEs will be assessed by investigators according to CTCAE.

Treatment-emergent adverse events are defined as AEs that:

- Emerge during treatment, having been absent at pretreatment; or
- Reemerge during treatment, having been present at pre-treatment but stopped prior to treatment; or
- Worsen in intensity during treatment relative to the pre-treatment state, when the AE is continuous.

An AE is treatment emergent if the start date/time of the event occurs any time on or after the first dose received on Day 1.

Adverse events that start within seven days after the last dose of study drug will be considered TEAEs.

The following types of summary will be provided by treatment using Randomized Safety population for each treatment phase separately:

1. Overview of TEAE
2. TEAEs by SOC, PT, and Maximum Severity
3. TEAEs by SOC and PT
4. Drug-Related TEAEs by SOC and PT
5. Drug-Related TEAEs by SOC, PT and Maximum Severity
6. TEAEs by Preferred Term in Descending Order

If a PT or SOC was reported more than once for a subject, the subject would only be counted once in the incidence for that PT or SOC.

In tabulation by severity grade,

- For a given SOC, only the most severe SOC for each subject will be included.
- For a given PT, only the most severe PT for each subject will be included.

In tabulations by relationship to study drug,

- For a given SOC, only the most related SOC for each subject will be included.
- For a given PT, only the most related PT for each subject will be included.

All AEs, TEAEs, AEs leading to treatment discontinuation will be provided in listings.

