8.2 Vital signs

For each continuous vital sign parameter, descriptive summary statistics for values observed at Baseline and at each scheduled timepoint, and for the change from Baseline will be presented. For this summary, the Baseline is the last non-missing value prior to the start of Fentanyl treatment. This summary will be presented in the randomized safety population.

Vital sign data will be provided in a listing for subjects in Randomized Safety population.

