8.3 Electrocardiogram (ECG)

For each continuous ECG parameter, descriptive summary statistics for values observed at Baseline and at each scheduled timepoint, and for the change from Baseline will be presented. For this summary, the Baseline is the last non-missing value prior to the start of Fentanyl treatment. This summary will be presented in the randomized safety population.

ECG data will be provided in a data listing for subjects in Randomized Safety population.

9 Pharmacodynamic Analysis (Part 2 Only)

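### The SAP's safety summaries, and its vital-sign and ECG listings, cover randomised subjects only, so anyone dosed in Part 1 and never randomised is left out

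*SAP*

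**What the plan says.** SAP 5.2 gives the only safety population; it "includes subjects who are randomized and receive at least 1 dose of the study drug". The randomisation row of the Part 2 flow chart (SAP 2.1, Table 2) places that step "Prior to study drug dosing in Period 1 only". The Part 1 flow chart (Table 1) has no such row.

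The safety sections then use this population:

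- SAP 8.1: "The following types of summary will be provided by treatment using Randomized Safety population for each treatment phase separately". Six TEAE summaries follow.
- SAP 8.2: the vital-sign summary is on the randomised safety population, and "Vital sign data will be provided in a listing for subjects in Randomized Safety population".
- SAP 8.3: the ECG summary is on the same population, and "ECG data will be provided in a data listing for subjects in Randomized Safety population".

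One output is not limited in this way. In 8.1, "All AEs, TEAEs, AEs leading to treatment discontinuation will be provided in listings", with no population named.

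Part 1 involves dosing. The protocol synopsis lists intravenous fentanyl as a Part 1 test treatment and intravenous saline placebo as a reference treatment for both parts. SAP Table 1 schedules vital signs around a saline infusion and a fentanyl infusion.

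**The concern.** Part 1 exists to select who enters Part 2, so subjects who are dosed and do not go on are a foreseeable result of the design. Read as written, the SAP gives no adverse event incidence for them and neither summarises nor lists their vital signs (which include SpO2) or ECGs.

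This bears on a stated objective. SAP 3.2 includes the safety and tolerability of fentanyl both with and without nalmefene or naloxone. Part 1 is where fentanyl is given with no study antagonist to follow, in a model that deliberately depresses respiration. An adverse event listing shows individual cases but gives no rate over a dosed denominator.

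**Working it through.** The plan gives no figure on this point, so the check compares the population named for each output with who can belong to it.

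**1. Can another defined population take in these subjects?** SAP 5.1 to 5.4 define four.

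| Population | Requires randomisation? | Restricted to dosed subjects? |
|---|---|---|
| Enrolled (5.1) | No | No |
| Randomized Safety (5.2) | Yes | Yes |
| Eligible Analysis Set (5.3) | Yes | Yes |
| Full Analysis Set (5.4) | Yes | Yes |

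Three of the four require randomisation; for the third row, the "eligible analysis set (EAS) include subjects/periods who are randomized, receive study drug". The remaining one does not help: "Enrolled population includes all subjects who signed informed consent". It therefore takes in screen failures, whom SAP 6.3 counts among discontinuations, and is not a dosed denominator.

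**2. Which outputs are restricted?**

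- Summaries: 6 (8.1) + 1 (8.2) + 1 (8.3) = 8.
- Listings: 1 (8.2) + 1 (8.3) = 2.

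**3. What is lost for each subject left out?** From SAP 2.1, Table 1:

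- Day 1 vital signs with SpO2: 1 before saline + 3 (fentanyl predose, 30 and 60 minutes) + 3 (end of infusion, then 2 and 4 hours) = 7 scheduled time points. Of these, 7 − 2 = 5 come after fentanyl starts. The table allows time points to be added, dropped or moved.
- ECG: Screening, Check-in and EOS = 3 visits, of which 1 (EOS) follows dosing.

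**4. Does other SAP wording override the restriction?**

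- SAP 6.1 asks for summaries by treatment within each part, but only as a default where nothing else is specified. Sections 8.1 to 8.3 do specify a population.
- SAP 8.1 refers to each treatment phase. If that means Part 2 alone, there is no Part 1 TEAE table. If it includes Part 1, the table holds only those Part 1 subjects who were later randomised.
- The output lists at the start of SAP section 6 name no population, so they do not displace the specific limits in section 8.
- SAP section 1 permits additional analyses but commits to none.

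**5. Was the exclusion intended?** Other sections suggest not. SAP 6.4 assigns a population for Qualification Phase demographics, SAP 10.1 defines a qualification baseline, SAP 10.2 defines a qualification Day 1, and SAP 2.1 describes Part 1 as having a treatment phase. Only the safety population lacks a Part 1 counterpart.

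**The case against.** The strongest reply accepts the literal reading and disputes how much it matters.

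- **No demonstrated consequence.** The number affected could be zero and the wording may be a slip. Both are true. But a slip in a population definition is still what the programmers will follow.
- **The counts include pre-dose data.** Two of the seven vital-sign points and two of the three ECGs precede fentanyl. This stands as a clarification, and the split is shown in the working. The pre-dose values still matter, because they supply the baseline.
- **Other outputs mitigate.** SAP section 6 promises a treatment exposure table and listing with no population limit. If produced for Part 1, these could be combined with the unrestricted adverse event listing to derive a crude incidence. This is fair for adverse events. It does nothing for vital signs or ECGs, and a reader should not have to build the rate by hand.
- **Part 2 also has fentanyl-only exposure** before each antagonist dose. This stands: Part 1 is not the sole source for the fentanyl-alone part of the objective.
- **The protocol may define a safety population.** The protocol text available ends with the schedule of assessments, so this could not be checked. The SAP states that it supersedes the protocol's statistical considerations, so its own definition governs.
- **A saline-only baseline rule covers a case the documents never describe.** That is so, but the rule follows once placebo counts as study drug, and it costs one clause.

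**Conclusion.** The concern holds. As written, the SAP leaves subjects dosed in Part 1 and never randomised out of 8 safety summaries and 2 listings, and no other defined population covers them.

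The number of subjects cannot be estimated. Part 1 has no stated size, no qualification rate is given, and the two documents differ on who may skip Part 1: the protocol synopsis names three earlier studies, SAP 2.1 only NAL1003. The number is zero if nobody is dosed in Part 1 or if everyone dosed there is later randomised.

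No direction of bias can be claimed. The qualification criteria are not in the available text, and the protocol synopsis shows that an uncertain qualification result can be technical, such as equipment function. These subjects do appear in disposition, in Qualification Phase demographics and in the adverse event listing. Laboratory, physical examination and local tolerability results are outside this point, because SAP section 8 assigns them no population. The primary comparison of minute ventilation is unaffected. The gap should be corrected, but it does not threaten the trial's main conclusion.

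**What to change.** - Add to SAP section 5 a Part 1 Safety Population: all subjects who receive any study drug (saline placebo or fentanyl) in Part 1, whether or not they are later randomised.
- Produce the Part 1 TEAE, vital-sign/SpO2 and ECG summaries and listings on it. Keep the Randomized Safety Population for Part 2.
- State in 8.1 that the phases reported separately include the Qualification Phase.
- State in 8.2 and 8.3 that, for a subject who receives saline only and so has no fentanyl start time, baseline is the last value before the saline infusion.

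The cost is one definition, one sentence in 8.1, one baseline clause in 8.2 and 8.3, and at most 8 extra summaries and 2 extra listings from data already collected. No study procedure changes.

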5.3 Eligible Analysis Set (EAS)

Twenty subjects will be expected to complete the study, each of whom will receive nalmefene or naloxone in different order after fentanyl -induced respiratory depression (OIRD).

For each period, eligible analysis set (EAS) include subjects/periods who are randomized, receive study drug, have at least 1 valid PD measurement, and their OIRDs are worse than baseline for MV and TCO₂. Note: baseline and OIRD for MV and TCO₂ may be different. Therefore, eligible analysis set for each PD parameter and period may be different.

To evaluate the treatment difference between nalmefene and naloxone, the same treatment under different periods will be pooled by averaging PD parameters from eligible data for each subject.

This analysis set will be used as primary analysis.

5.4 Full Analysis Set (FAS)

Full analysis set (FAS) includes subjects/periods who are randomized, receive study drug, and have at least 1 valid PD measurement for one individual period.

To evaluate the treatment difference between nalmefene and naloxone, the same treatment under different periods will be pooled by averaging PD parameters from eligible data for each subject.

This set will be used as sensitivity analyses. However, if it is determined that EAS is very similar to FAS, only EAS will be performed.

6 Statistical Considerations

All summaries and statistical analysis will be performed by SAS version 9.4 or later.

Following each administration of Nalmefene Autoinjector or Narcan, the reversal time course of the fentanyl induced respiratory depression for MV and TCO₂ will be evaluated.

The following data will be provided in the summary tables:

- Disposition
- Demographics and baseline characteristics
- Medical history
- Concomitant medications
- Treatment exposure
- Treatment emergent adverse events
- Derived pharmacodynamic (PD) parameters based on PD assessment data
 - Change in MV from opioid induced nadir (Opioid Induced Respiratory Depression (OIRD))
 - Maximum of reversal in MV
 - Time to maximum of reversal in MV

The summary figures/tables for PD assessment will include

- Individual profiles
- Treatment mean profiles
- Change from baseline and percent change from baseline in MV and TCO₂ from opioid induced nadir
- Change in MV from opioid induced nadir (Opioid Induced Respiratory Depression (OIRD))
- Maximum of reversal in MV
- Time to maximum of reversal in MV
- Time to onset
- Vital signs
- Physical examinations

The following data will be provided in data listings:

- Demographics and baseline characteristics
- Treatment exposure
- Medical history
- Prior and concomitant medication/therapy

- Treatment emergent adverse events
- Derived pharmacodynamic (PD) parameters
- Vital signs
- Physical examinations
- Electrocardiogram

6.1 General Statistical Procedures

Frequency distributions for categorical variables will be provided as number and percentage of subjects with a response in the category. Unless otherwise specified, percentages will be based on number of subjects in the given population as noted. Percentages will be reported to one decimal place.

The descriptive statistics for continuous variables will be number of subjects, mean, standard deviation (SD), median, minimum and maximum. Mean and median will be reported to 1 more decimal place than the raw data, while the SD will be reported to 2 more decimal places than the raw data. Minimum and maximum will be reported the same as the original data.

Unless otherwise stated, all statistical summary will be performed separately for each treatment in each part.

In general, all listings will be ordered by Part, subject ID and visit for available data unless otherwise specified in the footnote.

6.2 Statistical Hypotheses

Hypotheses #1: Non-inferiority Test

The null hypothesis is that Nalmefene (μ_T) is inferior to reference treatment (μ_R).

The alternative hypothesis is that Nalmefene is not inferior to reference treatment.

$$H_0: \mu_T - \mu_R \leq -0.5 \quad \text{vs.} \quad H_1: \mu_T - \mu_R > -0.5$$

Hypothesis #2: Superiority Test

The null hypothesis is that Nalmefene (μ_T) is not superior to reference treatment (μ_R).

The alternative hypothesis is that Nalmefene is superior to reference treatment.

$$H_0: \mu_T - \mu_R \leq 0 \quad \text{vs.} \quad H_1: \mu_T - \mu_R > 0$$

Statistical analysis will be performed for hypothesis #1 first, if noninferiority is met the analysis will proceed to hypothesis #2.

6.2.1 Multiplicity Adjustment

For the primary endpoint, the non-inferiority test will be performed first. If non-inferiority is achieved, superiority will be tested sequentially. Using this hierarchical test procedure, the comparison of the two treatments will be tested based on a one-sided alpha = 0.025.

The secondary endpoints will not be adjusted for multiplicity.

6.3 Subject Enrollment and Disposition

Number of subjects will be provided overall for Enrolled population for both Qualification Phase and Treatment Phase as follows:

Number of subjects enrolled

Number of subjects in randomized safety population

Number of subjects in full analysis population

Number of subjects completed study

Number of subjects completed treatment phase

Number of subjects discontinued (including screen failures)

Reasons for discontinuation

For the Randomized Safety population, the denominators for percentages are based on number of Enrolled population.

Enrollment information and disposition will be provided in a data listing.

6.4 Demographic and Other Baseline Characteristics

The following variables will be summarized overall using Enrolled population and randomized safety population.

- Age (years) at screening. If not reported, calculated as integer of (date of informed consent signed – date of birth)/365.25.
- Age category ($18 \leq \text{age} < 35$, $35 \leq \text{age} < 50$, $50 \leq \text{age} < 55$)
- Sex
- Race
- Ethnicity
- Height (cm)
- Weight (kg)
- BMI (body mass index, kg/m^2 , calculated as Weight (kg) / (Height (m) 2)
- Child-bearing potential (Yes, No, Not Applicable: Subject is Male)

Conversions for height and weight are as follows:

Height (cm) = Height (inches) \times 2.54

Weight (kg) = Weight (lb) \times 0.4536

The above demographics and baseline characteristics will be summarized for the Qualification Phase using the enrolled population and the Treatment Phase using randomized safety population.

Demographic characteristics will also be listed.

7 Efficacy Analysis

Not applicable.

8 Safety Analysis

8.1 Adverse Events

Adverse events (AEs) will be presented separately by treatment assignment. AEs will be coded using the most current version of MedDRA and will be classified by SOC and PT of MedDRA. Severity of AEs will be assessed by investigators according to CTCAE.

Treatment-emergent adverse events are defined as AEs that:

- Emerge during treatment, having been absent at pretreatment; or
- Reemerge during treatment, having been present at pre-treatment but stopped prior to treatment; or
- Worsen in intensity during treatment relative to the pre-treatment state, when the AE is continuous.

An AE is treatment emergent if the start date/time of the event occurs any time on or after the first dose received on Day 1.

Adverse events that start within seven days after the last dose of study drug will be considered TEAEs.

The following types of summary will be provided by treatment using Randomized Safety population for each treatment phase separately:

1. Overview of TEAE
2. TEAEs by SOC, PT, and Maximum Severity
3. TEAEs by SOC and PT
4. Drug-Related TEAEs by SOC and PT
5. Drug-Related TEAEs by SOC, PT and Maximum Severity
6. TEAEs by Preferred Term in Descending Order

If a PT or SOC was reported more than once for a subject, the subject would only be counted once in the incidence for that PT or SOC.

In tabulation by severity grade,

- For a given SOC, only the most severe SOC for each subject will be included.
- For a given PT, only the most severe PT for each subject will be included.

In tabulations by relationship to study drug,

- For a given SOC, only the most related SOC for each subject will be included.
- For a given PT, only the most related PT for each subject will be included.

All AEs, TEAEs, AEs leading to treatment discontinuation will be provided in listings.

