10.1 Definition of Baseline

For all evaluations unless otherwise noted, baseline is defined as the most recent non-missing measurement prior to or on the first administration of Fentanyl for qualification phase or each period during treatment phase, including unscheduled measurements. Baseline can be the same date as first dose, given the measurement is expected prior to first dose when only date information is available.

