10.2 Definition of Study Days

Unless otherwise noted, study days of an evaluation are defined as number of days relative to the first dosing date of Fentanyl of qualification or treatment phase which is designated as Day 1, and the preceding day is Day -1, the day before that is Day -2, etc.

- If evaluation date is on or after first dose date, then study days are calculated as
 - Evaluation date minus - first dose date of study drug + 1
- If evaluation date is before first dose date, then relative study days are calculated as
 - Evaluation date - first dose date of study drug

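### Does SAP 8.1 misattribute Part 2 adverse events that start after fentanyl but before that period's antagonist?

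*SAP*

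**What the plan says.** SAP 8.1 sets one start and one end for treatment emergence. An event is "treatment emergent if the start date/time of the event occurs any time on or after the first dose received on Day 1", and at the other end "Adverse events that start within seven days after the last dose of study drug will be considered TEAEs". On layout it says "Adverse events (AEs) will be presented separately by treatment assignment", with summaries "by treatment using Randomized Safety population for each treatment phase separately". When a preferred term or system organ class recurs, "the subject would only be counted once in the incidence for that PT or SOC". In the severity tables, "For a given PT, only the most severe PT for each subject will be included".

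The drug that starts the clock is not named in 8.1, but other sections point to it. SAP 10.2 counts study days "relative to the first dosing date of Fentanyl of qualification or treatment phase which is designated as Day 1". SAP 10.1 takes baseline before the "first administration of Fentanyl for qualification phase or each period during treatment phase". SAP 10.3 defines the first dose date by the earliest study drug given.

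In the Part 2 schedule (Table 2 in both documents) the antagonist is given about 10 minutes into the second fentanyl infusion. Neither SAP 8.1 nor any other supplied section assigns an event that starts before that moment.

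**The concern.** In the lead-in, fentanyl is titrated to depress ventilation and nothing given in that period opposes it yet. An event that starts then cannot have been caused by that period's antagonist. If it is nevertheless shown in the nalmefene or Narcan column, the column carries events that belong to fentanyl.

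Two of the table rules add to the worry. Because a preferred term counts once per subject, a lead-in event can hide a later one of the same kind. Because only the worst grade is kept, a lead-in event can set the grade shown.

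The secondary safety objective (SAP 3.2) also concerns fentanyl both alone and combined with an antagonist, and 8.1 defines no fentanyl-only column for Part 2. At stake would be the by-treatment safety tables: raised incidences in both antagonist columns, a blurred difference between them, and an attribution rule chosen after the events are known.

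**Working it through.** The question is mainly one of reading, with a little arithmetic on exposure.

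**1. Is a lead-in event treatment emergent?** SAP 10.2 ties Day 1 to the first fentanyl date. SAP 10.3 takes the earliest study drug. The SAP Introduction lists fentanyl among the test drugs. Together these make fentanyl the first dose, so lead-in events are in the tables for all four periods. The contrary reading, that the clock starts with the antagonist because Table 2 labels that row as study drug dosing, conflicts with 10.2 and 10.3.

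**2. Which column takes it?** SAP 2.1 randomises subjects to sequences of Narcan and nalmefene. SAP 5.3 uses the word treatment for those two. SAP 6.1 summarises by treatment within each part. Fentanyl is common to every Part 2 period and is not what is randomised. The column for a Part 2 period is therefore that period's antagonist regimen, lead-in included.

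**3. How long is the lead-in?** Inputs: total fentanyl time up to 230 min (protocol 1.1), second infusion 20 min, third infusion up to 90 min, antagonist about 10 min into the second infusion (protocol Table 2). With every step at its maximum:

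- first infusion = 230 − 20 − 90 = 120 min
- lead-in = 120 + 10 = 130 min
- share of fentanyl time = 130 / 230 = 57%, leaving 230 − 130 = 100 min after the antagonist
- share of the 72 h between dosing days (Days 1, 4, 7, 10) = 130 / 4,320 = 3.0%

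A first infusion of 120 min also matches the two-hour limit on fentanyl in Part 1. Part of the infusion detail is redacted, so 130 min is what the visible maxima imply, not a confirmed figure.

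**4. How many lead-ins?** The tables use the Randomized Safety population, up to 22 subjects (SAP 2.2): 22 × 4 = 88. For 20 completers it is 20 × 4 = 80.

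**5. Does the convention favour one antagonist?** Each antagonist is meant to be given in two of a subject's four periods, so with full completion each column takes 22 × 2 = 44 lead-ins. The lead-in procedure is the same whichever antagonist follows. Lead-in events should add to both columns alike. They can blur a difference, but nothing in the documents gives that blurring a direction.

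**6. Would splitting at the antagonist dose give a cleaner contrast?** Take the 130-min case and an antagonist not given in Period 4:

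- fentanyl-before-antagonist time per completer = 4 × 130 min = 520 min = 8.7 h
- time after that antagonist, to the next period = 2 × (72 h − 130 min) = 139.7 h
- ratio = 139.7 / 8.7 ≈ 16

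Crude incidences over windows that differ about 16-fold are not comparable. Fentanyl also continues after the antagonist, so the later columns remain mixed, and lead-ins in Periods 2 to 4 follow earlier antagonist doses. The split would be descriptive as well, with longer tables.

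**The case for a change.** The strongest case for a change is that several readings are possible and each gives a different table. Dosing days are three days apart and the tail is seven days, so a last-dose rule could even credit a lead-in event in Periods 2 to 4 to the previous antagonist. SAP 9.1 already separates the fentanyl-only stage for minute ventilation, so the authors saw the distinction and did not carry it into safety. The drug-related tables do not say which of the three drugs is meant. A definition would cost a sentence and one derived variable, and is more credible when fixed before lock.

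What stands: the rule is not written, and the once-per-term and worst-grade rules can let a lead-in event stand in for a later one.

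What does not stand is the step from there to a defect:

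- The sections on first dose and treatment agree well enough to lead an analyst to one reading.
- The piecewise handling in 9.1 serves smoothing of a continuous signal. It does not oblige the safety tables to follow.
- The objective in SAP 3.2 does not require the comparison to be made inside Part 2. Part 1 gives fentanyl with no antagonist under test. That evidence is limited, because the 8.1 tables use randomised subjects and some may skip qualification, but it is not absent.
- Only protocol sections 1.1 to 1.3 are supplied, so an attribution rule elsewhere in the protocol cannot be excluded.

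**Conclusion.** No change to the plan is needed. SAP 8.1 leaves an attribution detail unwritten, and the rest of the SAP leads to a sensible way of filling it: Part 2 columns are period regimens, fentanyl plus nalmefene and fentanyl plus Narcan, with the clock starting at fentanyl. That convention keeps the randomised comparison, because both regimens have the same lead-in. A table footnote naming the convention is ordinary programming practice.

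The exposure is real but bounded: up to 88 lead-ins, each about 130 min if the infusions run to their stated maxima. The effect on displayed incidence cannot be sized, since the documents give no adverse event rates. The tables are descriptive, no direction of bias is shown, and the primary analysis does not use them. All events go into listings, and 8.1 already works with start date and time, so lead-in events can be picked out later.

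The conclusion rests on two assumptions: that first dose means fentanyl, as SAP 10.2 and 10.3 indicate, and that the lead-in is run the same way before either antagonist.
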